6.4. Data protection and patient’s privacy	14
7. Publication Policy	15
8. Bibliography	15

1. Background

Inflammatory bowel diseases (IBDs), such as Crohn's disease (CD) and ulcerative colitis (UC), are chronic and debilitating conditions which affect the gastrointestinal tract and are characterized by a relapsing-remitting course [1]. Their pathogenesis is multifactorial, likely triggered by a dysregulated immune response to the gut microbiota in genetically susceptible individuals [2,3].

Traditionally, the management of IBD patients involved a broad spectrum of anti-inflammatory drugs, including 5-aminosalicylic acid drugs, steroids, and non-targeted immunosuppressants [4,5]. However, over the past two decades, with an increased understanding of the underlying disease mechanisms, there has been a therapeutic revolution, including biological therapies and small molecules targeting the adaptive immune system [6].

Since the late 1990s, the emergence of TNF inhibitors (such as infliximab and adalimumab) has represented a breakthrough in the treatment and disease control. These inhibitors have demonstrated excellent efficacy in inducing and maintaining remission, preventing disease complications, and achieving mucosal healing [7]. However, data from the literature indicate that up to 30% of patients do not respond to initial therapy with TNF inhibitors, and up to 50% lose response over time, with 10% ultimately requiring surgery [8]. Consequently, there is an urgent need to develop new molecules targeting different molecular targets.

New drugs with different signaling pathways for intestinal inflammation have been developed, targeting molecules such as $\alpha 4\beta 7$ integrin, Janus kinase (JAK), and interleukin 12 and 23 (IL-12/IL-23). In particular, studies on murine models have highlighted the critical role of IL-12 and IL-23 in promoting various inflammatory conditions, including colitis [9]. This understanding has spurred the development of new molecules targeting this pathway.

IL-12, primarily produced by dendritic cells, macrophages, and neutrophils in response to antigens, plays a pivotal role in guiding T-cell differentiation towards the Th1 interferon-gamma-producing lineage. In contrast, IL-23, formed by a complex of IL-12p40 and IL-23p19 subunits, plays a crucial role in Th17 cell differentiation and activates inflammatory cascades via JAK and STAT pathways [10–12]. Dysregulation of IL-23 may contribute to the development or exacerbation of intestinal inflammation by regulating effector cytokines such as IL-22 [10,13]. In patients with Crohn's disease, elevated levels of IL-23 are typically found in the mucosal lining. Additionally, genome-wide association studies have highlighted a significant link between variations in the IL-23 or IL-23 receptor (IL-23R) gene and the development of inflammatory bowel diseases [14–17]. Finally, variants of the IL-23R gene have been observed to influence the levels of IL-22 in the bloodstream, which in turn have been linked to the severity of the disease.

This understanding marks a turning point in our knowledge of IBD pathogenesis and has led to a growing interest in selectively blocking IL-23 [12,18]. Efforts have been directed towards developing increasingly selective drugs to minimize off-target/side effects and maximize efficacy [19].

The first generation of treatments involves therapy directed at anti-IL-12p40, with efficacy attributed to the inhibition of IL-23 rather than direct blocking of IL-12 [11]. Ustekinumab, a p40 subunit IgG1k inhibitor of IL12/23, has been a notable candidate in this category, demonstrating efficacy and safety for both CD and UC [20–22].

The second generation of selective anti-IL-23 therapies targets IL-23p19 and showed greater effectiveness compared to ustekinumab in other immune-mediated conditions, such as plaque psoriasis [23,24]. The rationale for specifically targeting the p19 subunit of IL-23 is to enhance safety by preserving the normal IL-12-mediated Th1 immune response, crucial for defending against intracellular pathogens [25]. This approach aims to maintain efficacy achieved with p40 antibodies while avoiding potential disruptions to the immune response [22]. Indeed, the IL-12-mediated Th1 response has been suggested to have a more significant impact on susceptibility to certain diseases, such as mycobacterial infections, compared to the IL-23-mediated Th17 response [26]. Similar relationships have been observed with other pathogens. By selectively targeting IL-23p19 while leaving IL-12 intact, host immunity against a variety of pathogens could be preserved [11,22]. However, despite belonging to the same drug category, these therapies have different molecular attributes that may result in differences in clinical efficacy.

Risankizumab, a monoclonal antibody targeting the IL-23 p19 subunit, has recently been approved for the treatment of Crohn's Disease by hindering its interaction with the IL-23R complex. In a randomized, double-blinded, phase 2 trial involving patients with moderate to severe Crohn's disease, intravenous induction therapy with risankizumab proved well-tolerated and effective at doses of 200 mg and 600 mg, regardless of patients' prior exposure to TNF antagonist therapy or vedolizumab [27]. Furthermore, two phase 3 studies, ADVANCE and MOTIVATE, showed that risankizumab was well-tolerated and led to significant early improvements compared to placebo across primary and secondary endpoints, in patients with moderate to severe Crohn's disease, irrespective of prior treatment history. IL-22, serving as a marker of IL-23 activity, decreased at week 12 with risankizumab treatment (600 mg and 1200 mg) but remained unchanged with placebo. Early symptom relief was associated with reductions in CRP and faecal calprotectin. The safety profile of risankizumab in Crohn's disease was consistent with previous studies in other conditions, with no new safety concerns identified [28].

Notably, previous literature revealed different rates of efficacy and effectiveness respectively assessed by randomized clinical trials (RCTs) and real-life studies for previously approved IBD biological drugs. Much of this variability stems from the strict inclusion and exclusion criteria employed in RCTs to select patients, which often exclude a significant portion of real-life patient. As a result, findings from RCTs may not always reflect real-world clinical practice. To address this gap, we established this study to assess the effectiveness of risankizumab in a multicenter, real-world cohort of CD patients.

Our study will encompass a retrospective cohorts of CD patients who is initiating biological treatment with risankizumab across various secondary and tertiary IBD centers in Italy with the objective to assess clinical, endoscopic and radiologic effectiveness of this promising new treatment in real-life CD patients.

2. Study aims

1. Primary aims

To evaluate the percentage of patients achieving the steroid-free clinical-practice deep remission of CD after 12 months from baseline of treatment with risankizumab (defined as the combination of patient reported outcomes (PRO) (patients reported abdominal pain ≤ 1 and average stool consistency ≤ 5 on Bristol Stool Scale without use of oral/intravenous steroids (prednisone-equivalent or budesonide) in the last 3 months) with an objective parameter of inflammation.

Faecal calprotectin < 150 mcg/g, OR Simple Endoscopic Score for Crohn's Disease (SES-CD) ≤ 4 and at least a 2-point reduction vs baseline and no subscore > 1 in any individual variable, OR transmural healing at MRI/CT scan enterography or intestinal ultrasound, defined as bowel wall thickness (BWT) ≤ 3 mm with no signs of active disease.

2. Secondary aims

1. To evaluate the percentage of patients achieving the steroid-free CPDR of CD after 6 and 24 months of risankizumab.
2. To evaluate the percentage of patients achieving clinical remission of CD (defined as HBI < 5) after 3 months, 12 months and 24 months of risankizumab. This aim will be evaluated only in patients with an HBI > 5 at baseline.
3. To evaluate the percentage of patients showing clinical response of CD (defined as a reduction of the HBI of at least 3 points from baseline) after 3 months, 6 months, 12 months and 24 months of risankizumab.
4. To evaluate the percentage of patients achieving endoscopic remission of CD (defined as SES-CD ≤ 4 and at least a 2-point reduction vs baseline and no subscore > 1 in any individual variable) after 3 months, 6 months, 12 months and 24 months of risankizumab.
5. To evaluate the percentage of patients showing endoscopic response of CD (defined as a greater than 50% decrease in SES-CD from baseline (or for isolated ileal disease and a baseline SES-CD of 4, at least a 2-point reduction from baseline) after 3 months, 6 months, 12 months and 24 months of risankizumab.

6. To evaluate the percentage of patients achieving the steroid-free “deep remission” of CD, defined as the combination of clinical remission and endoscopic remission according to the above mentioned criteria (PMID: 26303131) after 6 months, 12 months and 24 months of risankizumab.
7. To evaluate the percentage of CD patients achieving transmural healing at CT-scan or MRI enterography or at intestinal ultrasound (defined as a BWT \leq 3 and normal parietal contrast enhancement or color Doppler signal (CDS) or absence of hyperemia) after 3 months, 6 months, 12 months and 24 months of risankizumab.
8. To evaluate the percentage of patients showing response of CD at radiological exams, including CT-scan or MRI enterography and intestinal ultrasound (defined as a decrease in BWT by 25% from baseline or 2.0 mm, or greater than 1.0 mm with a decrease in parietal contrast enhancement or in CDS assessed by the modified Limberg score of one grade) after 3 months, 6 months, 12 months and 24 months of risankizumab.
9. To assess the variation of C-reactive protein (CRP) after 3 months, 6 months, 12 months and 24 months of treatment with risankizumab in CD patients.
10. To identify clinical, endoscopic or radiologic predictors of deep remission in CD at 12 months and 24 months.
11. To evaluate the percentage of patients achieving control of extraintestinal manifestation at 3 months, 6 months, 12 months and 24 months.
12. To compare the efficacy of risankizumab, as assessed according to the primary endpoint of the study, when used as second, third or fourth line of biological treatment.
13. To assess the safety of risankizumab during the entire study period.

2. Study endpoints

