2.2. Secondary endpoints

1. Percentage of patients achieving the CPDR of CD after 6 and 24 months of risankizumab.
2. Percentage of patients achieving clinical remission of CD (defined as HBI < 5) after 3 months, 6 months, 12 months and 24 months of risankizumab.
3. Percentage of patients showing clinical response of CD (defined as a reduction of the HBI of at least 3 points from baseline) after 3 months, 6 months, 12 months and 24 months of risankizumab. This endpoint will be assessed only in patients with an HBI > 5 at baseline.
4. Percentage of patients achieving endoscopic remission of CD (defined as SES-CD \leq 4 and at least a 2-point reduction vs baseline and no subscore >1 in any individual variable) after 3 months, 6 months, 12 months and 24 months of risankizumab.
5. Percentage of patients showing endoscopic response of CD (defined as a greater than 50% decrease in SES-CD from baseline (or for isolated ileal disease and a baseline SES-CD of 4, at least a 2-point reduction from baseline) after 3 months, 6 months, 12 months and 24 months of risankizumab.
6. Percentage of patients achieving the steroid-free “deep remission” of CD, defined as the combination of clinical remission and endoscopic remission according to the above-mentioned criteria (PMID: 26303131) after 6 months, 12 months and 24 months of risankizumab.
7. Percentage of CD patients achieving transmural healing at CT-scan or MRI enterography or at intestinal ultrasound (defined as a BWT \leq 3 and normal parietal contrast enhancement or color Doppler signal (CDS) or absence of hyperemia) after 3 months, 6 months, 12 months and 24 months of risankizumab.
8. Percentage of patients showing response of CD at radiological exams, including CT-scan or MRI enterography and intestinal ultrasound (defined as a decrease in BWT by 25% from baseline or 2.0 mm, or greater than 1.0 mm with a decrease in parietal contrast enhancement or in CDS assessed by the modified Limberg score of one grade) after 3 months, 6 months, 12 months and 24 months of risankizumab.

9. Variation of C-reactive protein (CRP) after 3 months, 6 months, 12 months and 24 months of treatment with risankizumab in CD patients.
10. Identification of clinical, endoscopic or radiologic predictors of deep remission in CD at 12 months and 24 months.
11. Percentage of patients achieving control of extraintestinal manifestation at 3 months, 6 months, 12 months and 24 months.

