4.2. Inclusion criteria

The participants must fulfill the following criteria for participating in the study:

1. Age of at least 18 years.
2. Patients with a previous diagnosis of CD at least 3 months before baseline.
3. Patients who have failed at least one advanced (biological or small molecule) therapy for CD and who have experienced failure to at least one mechanism of action (failure is defined as primary failure, secondary failure, or intolerance).
4. Patients, with any grade of clinical or endoscopic disease activity who have started a therapy with risankizumab for CD based on clinical practice indication (primary loss of response, secondary loss of response, intolerance to the previous drug).
5. Written informed consent certifying the willingness of the subject to participate to the study.

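### The secondary aims and secondary endpoints swap the baseline HBI > 5 restriction between clinical remission and clinical response, so each outcome has two conflicting denominators

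*Protocol*

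**What the plan says.** **Study aims, secondary aims 2 and 3.** Aim 2 is "clinical remission of CD (defined as HBI < 5) after 3 months, 12 months and 24 months of risankizumab", followed by "This aim will be evaluated only in patients with an HBI > 5 at baseline". Aim 3 reads "To evaluate the percentage of patients showing clinical response of CD (defined as a reduction of the HBI of at least 3 points from baseline", at 3, 6, 12 and 24 months, with no condition on baseline HBI.

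**Section 2.2, secondary endpoints 2 and 3.** Endpoint 2 is "Percentage of patients achieving clinical remission of CD (defined as HBI < 5) after 3 months, 6 months, 12 months and 24 months of risankizumab", with no condition on baseline HBI. Endpoint 3 uses the same 3-point definition of response and adds "This endpoint will be assessed only in patients with an HBI > 5 at baseline".

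**Section 4.2, inclusion criterion 4.** The cohort takes "Patients, with any grade of clinical or endoscopic disease activity who have started a therapy with risankizumab for CD". Intolerance to the previous drug is one of the accepted reasons for starting.

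Section 4.4 defines no analysis set for the HBI outcomes, and no other section says whether the aims or the endpoints take precedence.

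**The concern.** The same restriction appears in both lists but is attached to a different outcome in each. An analyst following the aims and an analyst following section 2.2 would use different denominators for remission, and again for response. Both would be following the protocol.

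Choosing one section does not solve the problem, because each leaves one outcome on an awkward denominator. Under section 2.2, a patient who enters below HBI 5 and stays there counts as having achieved remission. Under the aims, a patient who enters at HBI 0 to 2 is in the response denominator but cannot meet the definition.

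The study is retrospective, so outcome data may already exist when the denominator is settled. That is a reason to settle it in writing beforehand.

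**Working it through.** **1. The two sections side by side**

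| Outcome | Study aims | Section 2.2 |
|---|---|---|
| Remission (HBI < 5): denominator | baseline HBI > 5 | all patients |
| Remission: visits (months) | 3, 12, 24 | 3, 6, 12, 24 |
| Response (fall of 3 or more): denominator | all patients | baseline HBI > 5 |
| Response: visits (months) | 3, 6, 12, 24 | 3, 6, 12, 24 |

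**2. What the definitions imply by baseline HBI**

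- HBI 0 to 2: already below 5, and cannot fall by 3.
- HBI 3 or 4: already below 5, but can fall by 3 (3 to 0, 4 to 1).
- HBI 5: not in remission. Can remit (5 to 4) or respond (5 to 2), but is excluded wherever the > 5 rule applies.
- HBI 6 or more: counted under every version.

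**3. The plan's own figures**

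The protocol prints no figure for the HBI outcomes. Its one worked precision figure (section 4.4: width 0.28945 at n = 50 and proportion 0.5) concerns the primary endpoint. It reproduces as an exact Clopper-Pearson interval: 25 of 50 gives 0.35527 to 0.64473, width 0.28945. It is not in dispute. By the same method, the width at the expected 200 patients is 0.143, or about ±7 points.

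**4. Illustration A: all patients against patients not in remission at baseline (HBI of 5 or more)**

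All inputs are assumed. Let p be the share below 5 at baseline, m the share of those still below 5 at the visit, and r = 0.50 the remission rate in the rest.

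- All-patient rate = p × m + (1 − p) × r, so the gap to active patients = p × (m − r).
- Low end: 0.20 × 0.75 + 0.80 × 0.50 = 0.55, a gap of 5 points.
- Middle: 0.30 × 0.85 + 0.70 × 0.50 = 0.605, a gap of 10.5 points.
- High end: 0.40 × 0.95 + 0.60 × 0.50 = 0.68, a gap of 18 points.

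**5. Illustration B: all patients against the protocol's own > 5 cut-off**

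Again all inputs are assumed. Baseline shares (HBI 4 or less / exactly 5 / above 5) run from 20/5/75% to 60/10/30%.

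- Remission is assumed at 80-90% / 50-70% / 50%. Under the aims the rate is 50%. Under section 2.2 it runs from 0.20 × 0.80 + 0.05 × 0.50 + 0.75 × 0.50 = 0.56 to 0.60 × 0.90 + 0.10 × 0.70 + 0.30 × 0.50 = 0.76.
- Response is assumed at 10% / 50% / 60%. Under section 2.2 the rate is 60%. Under the aims it runs from 0.20 × 0.10 + 0.05 × 0.50 + 0.75 × 0.60 = 0.495 down to 0.60 × 0.10 + 0.10 × 0.50 + 0.30 × 0.60 = 0.29.
- Adding patients at exactly 5 moves remission by 0 to 5 points (at most (0.10 × 0.70 + 0.30 × 0.50) / 0.40 = 0.55 against 0.50). It moves response by about 1 to 3 points.
- Of 200 patients, the denominator would be 60 to 150 with HBI > 5 and 80 to 160 with HBI of 5 or more.

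**6. The 6-month visit**

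Section 5.1 schedules a 6-month time point and collects the HBI items at every time point. Aim 6 needs clinical remission at 6 months as part of deep remission. The intended visit can therefore be recovered, and its absence from aim 2 looks clerical.

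**The case against.** The strongest reply has four parts.

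- **Scope.** The outcomes are descriptive and secondary. This stands: the primary endpoint uses patient-reported items and objective markers rather than HBI, so neither it nor its precision calculation is touched.
- **Bias.** The proportion below HBI 5 among all treated patients is a legitimate quantity in a single-group cohort. It misleads only if labelled as remission achieved. This also stands. The defect is that the population is undefined, not that one rate is wrong in itself.
- **Size.** The protocol gives no HBI distribution, no maintenance rate and no HBI remission rate, so every figure above is assumed. This stands. In addition, illustration A compares all patients with HBI of 5 or more, whereas the conflict in the text is between all patients and HBI > 5.
- **The > 5 cut-off.** A reader might infer that leaving out HBI 5 is a further contradiction that makes the denominators wrong. The documents do not support that. Both sections use > 5, and an entry threshold one point above the remission cut-off is unusual but coherent. It is a minor boundary point.

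None of this removes the contradiction. Nor is it a detail left to a statistical analysis plan: the protocol states two opposite rules, and any later plan could follow only one of them.

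**Conclusion.** The contradiction holds. Clinical remission and clinical response each have two incompatible denominators, and neither section can be adopted whole.

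The size cannot be known from the protocol. Under the assumptions of illustration A, unrestricted remission is 5 to 18 points above the rate in active patients. Under those of illustration B, the two sections give 50% against 56-76% for remission and 60% against 29-50% for response. For scale, sampling error at 200 patients is about ±7 points, so the choice of section can matter more than chance. These figures show what is possible and are not estimates.

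Two stronger conclusions might be drawn and are not supported. One is that the study's main result is compromised; it does not depend on HBI. The other is that the denominator was left open so that the better rate could be picked; the text shows only an inconsistency. The ambiguity may carry into deep remission (endpoint 6), which reuses the clinical remission criteria, and so into its predictors (endpoint 10).

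**What to change.** - State one analysis set for remission and one for response, in identical words in the aims and in section 2.2. Restrict both to patients with active disease at baseline.
- Preferably define active as HBI of 5 or more, the complement of the protocol's own remission definition, so that patients at exactly 5 are not lost.
- If a rate in all patients is wanted, report it separately as the proportion with HBI below 5, not as remission achieved.
- Say whether the baseline restriction also applies to the clinical part of deep remission.
- As a side note, add the 6-month visit to aim 2.

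**Cost.** A few sentences of text. The denominators become smaller than in the unrestricted versions (illustratively 80 to 160 of 200), with wider intervals: the exact 95% width at a proportion of 0.5 is 0.203 at n = 100 against 0.143 at n = 200. Against the existing > 5 rule, HBI of 5 or more enlarges the denominator. Patients at HBI 3 or 4, who could in principle fall by 3 points, leave the response analysis, as they already do under section 2.2.

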2.1. Primary endpoint

Primary endpoint of the study is the proportion of CD patients achieving steroid-free clinical-practice-deep remission (CPDR) after 12 months from baseline of treatment with Risankizumab, defined as the combination of:

patient reported outcomes (PRO) (patients reported abdominal pain \leq 1 and average stool consistency \leq 5 on Bristol Stool Scale without use of oral/intravenous steroids (prednisone-equivalent or budesonide) in the last 3 months)

AND an objective parameter of inflammation:

Faecal calprotectin <150 mcg/g, OR SES-CD \leq 4 and at least a 2-point reduction vs baseline and no subscore >1 in any individual variable, OR transmural healing at MRI/CT scan enterography or intestinal ultrasound, defined as BWT \leq 3 mm with no signs of active disease.

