12. Comparison between the efficacy of risankizumab, as assessed according to the primary endpoint of the study, when used as second, third or fourth line of biological treatment.
13. Assessment of the safety of risankizumab during the entire study period.

3. Study design and investigational plan

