3.1. Overall study design

This is a multicenter, retrospective observational study with drug, including patients fulfilling inclusion and exclusion criteria, whom data required for the protocol are available.

We will include consecutive patients affected by CD, who have initiated Risankizumab and failed (already exposed) at least one mechanism of action (for anti TNF-alpha several molecules are allowed), until January 2024.

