4.4. Sample size evaluation and statistical analysis

Based on the real-life study design and on the primary endpoint, which foresees a descriptive evaluation of remission rates according to each therapy line considered, we present diverse scenarios of potential sample size (from 50 till 300 by 25), and related confidence intervals in order to detect a CPDR at 12 months of 50-55 and 60% according to the evidence available from the current literature on the drugs under investigation. All scenarios are assessed according to a single group study design with a two-sided 95% confidence interval for a single proportion. A table with all potential scenarios will be provided as attachment.

As an example, such single-group design to obtain a two-sided 95% confidence interval for a single proportion, assuming a sample proportion of 0.5, with a sample size of 50, would produce a confidence

interval width of 0.28945, i.e., 0.5 ± 0.145 . The confidence interval widths were computed using PASS 2022, version 22.0.4 [29].

Based on the data available to the participating centers (for the retrospective phase) and the recruitment capabilities of the centers during the enrollment period, we expect to enroll 200 subjects with Crohn disease in this retrospective study.

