5.1. Experimental procedures

Data will be retrieved from the electronic archives of all participating center. Each patient will be identified by a number who will avoid double insertion of the same patient and will ensure the anonymization of data. Collected data will be entered in an electronic case report form (RedCap) and will follow all the requirements of Italian privacy policy.

In depth, the standard points will be: induction of therapy (T0 - week 0); 12 weeks after the beginning of therapy (T1), 6 months after the beginning of therapy (T2), 12 months after the beginning of therapy (T3), and 24 months after the beginning of therapy (T4).

The following clinical data at each time-point will be collected, to calculate Harvey Bradshaw Index – general well-being, abdominal pain, number of liquid/soft stools, abdominal mass and extraintestinal manifestations for CD.

Endoscopic or radiologic monitoring of disease activity respectively by ileocolonoscopy or intestinal ultrasound or CT-scan or MRI-enterography will be collected at baseline and at 12 and 24 months after the start of therapy. Endoscopic disease activity will be assessed according to the SES-CD.

Steroid-free clinical practice deep remission (CPDR) will be defined based on patient reported outcomes (PRO) combined with an objective parameter of inflammation:

- patients reported abdominal pain ≤ 1 and average stool consistency ≤ 5 on Bristol Stool Scale without use of oral/intravenous steroids (prednisone-equivalent or budesonide) in the last 3 months;

AND

- Faecal calprotectin <150 mcg/g, OR SES-CD \leq 4 and at least a 2-point reduction vs baseline and no subscore >1 in any individual variable, OR transmural healing at MRI/CT scan enterography or intestinal ultrasound, defined as BWT \leq 3 mm with no signs of active disease.

6. Ethical aspects

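### As worded, the primary remission endpoint counts patients who stopped risankizumab and reached remission on another advanced therapy or after resection, yet it is read as risankizumab efficacy

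*Protocol*

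**What the plan says.** Protocol section 3.1 defines the cohort by drug start: "We will include consecutive patients affected by CD, who have initiated Risankizumab", after failure of at least one mechanism of action.

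Section 2.1 makes the primary endpoint the "proportion of CD patients achieving steroid-free clinical-practice-deep remission (CPDR) after 12 months from baseline of treatment with Risankizumab". CPDR is written out in full in the primary aim (section 2), in 2.1 and in 5.1, each time with the same elements:
- limits on abdominal pain and stool consistency;
- a steroid condition, "without use of oral/intravenous steroids (prednisone-equivalent or budesonide) in the last 3 months";
- one objective criterion out of calprotectin, SES-CD or transmural healing.

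None of the three versions mentions continued risankizumab, another advanced therapy or surgery.

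Section 5.1 sets the visit for the primary endpoint as time since the start: "12 months after the beginning of therapy (T3". The same sentence sets the 6-month (T2) and 24-month (T4) visits in the same way.

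In 2.2, the first secondary endpoint is "Percentage of patients achieving the CPDR of CD after 6 and 24 months of risankizumab". Endpoints 2 to 8 use similar timing words, and endpoint 9 (CRP) refers to "24 months of treatment with risankizumab in CD patients". Endpoint 12 is "Comparison between the efficacy of risankizumab, as assessed according to the primary endpoint of the study", by line of biological treatment.

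**The concern.** The definition names one disqualifying treatment, steroids, and stops there. Two kinds of patient show the consequence.
- One stops risankizumab at month 4, starts another biologic or small molecule, and at month 12 meets the symptom limits with a calprotectin below 150 mcg/g.
- The other has the diseased segment resected at month 6 and at month 12 meets the symptom limits, with bowel wall thickness within 3 mm and no signs of active disease.

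If neither took steroids in the last 3 months, both satisfy every stated element and count as remission.

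That would be acceptable for an outcome labelled as status regardless of later treatment. Endpoint 12, however, presents the same measure as the drug's efficacy by line. Remission produced by the next drug or by surgery is not risankizumab efficacy. Patients in different lines may also have different options left, so the distortion need not be equal across the lines compared.

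The study is retrospective, so outcomes may already be in the archives when the rule is settled. That is a reason to settle it in writing before extraction.

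**Working it through.** **Step 1: the wording, element by element.**

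| Question | What the Protocol states | Where |
|---|---|---|
| Who is in the cohort? | Patients who started risankizumab | 3.1 |
| When is status read? | 12 months after the start of therapy (T3) | 2.1, 5.1 |
| Which treatment disqualifies? | Oral or intravenous steroids in the last 3 months | section 2 aims, 2.1, 5.1 |
| Must risankizumab be ongoing? | Not stated | – |
| Does another advanced therapy or a resection disqualify? | Not stated | – |
| How is the result used? | As risankizumab efficacy by line | 2.2, endpoint 12 |

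Applied as written, the rule can score a switched or resected patient as a success.

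**Step 2: the plan's precision figure.** Section 4.4 uses a "two-sided 95% confidence interval for a single proportion" and gives a width of 0.28945 for n = 50 and a proportion of 0.5. The exact Clopper-Pearson interval for 25/50 is 0.35527 to 0.64473, a width of 0.28945, so the figure reproduces and is not in dispute. By the same method at the expected n = 200:
- proportion 0.50: 0.4287 to 0.5713, width 0.1427, half-width 0.071;
- proportion 0.60: 0.5285 to 0.6685, width 0.1399, half-width 0.070.

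**Step 3: how far the rule can move the rate.** Let P be the 12-month rate as worded, d the share off risankizumab at month 12, and r the share of those in CPDR. Counting stopping as failure gives

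rate = P − d × r,

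so the shift is d × r. P = 50% and 60% are the ends of the planning range in 4.4. The documents give neither d nor r. The ranges d = 10-30% and r = 20-50% are assumptions.

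| d | r | Shift d × r (points) | Rate if P = 50% | Rate if P = 60% |
|---|---|---|---|---|
| 10% | 20% | 2 | 48% | 58% |
| 10% | 50% | 5 | 45% | 55% |
| 20% | 30% | 6 | 44% | 54% |
| 20% | 40% | 8 | 42% | 52% |
| 30% | 30% | 9 | 41% | 51% |
| 30% | 50% | 15 | 35% | 45% |

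At n = 200 this is between 200 × 0.02 = 4 and 200 × 0.15 = 30 patients. The shift passes the 7-point half-width only when d × r exceeds 0.07. Within the assumed ranges that does not happen at d = 10% (at most 5 points). It does at d = 20% with r = 40%, and at d = 30% with r = 30%.

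**The case against.** **The text never says that remission after a switch or surgery counts.** True. It follows from a definition that lists its conditions in three places and bars only steroids. The primary wording could loosely be read as 12 months on drug, but T3 in 5.1 is time since the start.

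**Handling of stopping and switching is commonly left to the statistical analysis plan, which is not shown.** This stands for details such as censoring in the Kaplan-Meier and Cox analyses, which are not criticised here. It does not cover the endpoint definition itself, which the Protocol fixes. A later plan that disqualified switched patients would be changing that definition.

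**Status regardless of later treatment is a legitimate target in a real-world cohort.** It is, if chosen and labelled as such. It does not fit endpoint 12, which calls the result the drug's efficacy.

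**The size is wholly assumed.** This stands. The low end lies well inside the planned precision, and 15 points needs both extremes at once. The background figures on non-response and surgery concern TNF inhibitors and do not supply d. Nor does the Protocol say that outcomes are collected after risankizumab stops, which the shift requires.

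**A stronger reading is tempting.** A reader might take months of risankizumab in secondary endpoints 1 to 8, and the similar phrase in endpoint 9, as time on drug. The 6- and 24-month CPDR rates would then be completer rates that drop patients who stopped, and would not be comparable with the 12-month rate. The documents do not support this. Section 5.1 ties T2, T3 and T4 to the start of therapy in one sentence, and endpoints 2 to 8 use the same phrase for the 12-month visit. Nothing says that patients who stopped leave the denominator. Where the Protocol restricts a denominator it says so, as with the baseline HBI condition in section 2 and in 2.2. The phrase is loose wording to be harmonised.

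**Conclusion.** The point holds for the definition of CPDR. It applies to all initiators, is read by time since the start, and excludes only recent steroid use. Applied literally, it credits risankizumab with remission reached on another advanced therapy or after resection, and endpoint 12 then reads the result as efficacy by line.

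The amount cannot be derived from the documents. Under the assumed 10-30% off drug and 20-50% of those in remission, it is 2 to 15 points, against a half-width of about 7 points at n = 200. The choice of rule may therefore matter more than sampling error, or may be minor. No number in the Protocol is wrong.

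The definition should be settled before data are extracted, but the unknown size does not justify calling this a decisive flaw.

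**What to change.** In 2.1, 2.2 and 5.1, and in the matching primary aim:
- Count CPDR as met only if the patient is still receiving risankizumab at the time point, with no other advanced therapy started and no Crohn's-related resection or stoma since T0.
- Count patients who stopped, switched or had such surgery as not in CPDR.
- Use all patients who initiated risankizumab as the denominator.
- Word every time point as months from the start of risankizumab, in line with the schedule in 5.1.
- Report status regardless of treatment as a supportive figure, labelled as such.

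These are rules for classifying outcomes in the analysis and leave patient care unchanged. The cost is the change of wording plus stop date, next therapy and surgery fields, extracted from the same archives where not already captured. The reported remission rates may be somewhat lower.
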